#### 6.8.2 Adverse Events

All AEs will be classified by system organ class and preferred term using the MedDRA. TEAEs will be tabulated in a manner which provides information about the incidence of TEAEs for the entire study. For incidence reporting, if a subject reported more than one TEAE that was coded to the same system organ class or preferred term, the subject will be counted only once for that

specific system organ class or preferred term. An overview of AEs, which includes subject incidence of AEs, TEAEs, treatment-related TEAEs, TEAEs by severity, SAEs, deaths, and AEs leading to discontinuation of study drug, will be presented.

All information pertaining to AEs noted during the study will be listed by subject and will include a verbatim description of the event as reported by the investigator, as well as the preferred term, system organ class, start date, end date (if ended), seriousness, severity, action taken regarding the study drug, outcome, and relationship to the study drug. In addition, a listing of subjects who prematurely discontinued study drug due to AEs will be provided.

SAEs will be listed and summarized in a similar manner to AEs.

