8.8 Safety Analyses

8.8.1 Adverse Events

All AEs will be classified by system organ class and preferred term using the Medical Dictionary for Regulatory Activities (MedDRA). TEAEs will be tabulated in a manner which provides information about the incidence of TEAEs for the entire treatment period as well as by time period in order to understand the evolution of TEAEs over time. Thus, in addition to the TEAE analysis over the entire 12-month treatment time, results will be presented for the following periods: 0 to 4 weeks, > 4 to 12 weeks, > 12 to 28 weeks, > 28 weeks to 36 weeks, > 36 to end of treatment, and end of treatment to end of the study (including by weekly periods from end of treatment to end of study). For incidence reporting, if a subject reported more than one TEAE that was coded to the same system organ class or preferred term, the subject will be counted only once for that specific system organ class or preferred term. An overview of AEs, which includes subject incidence of AEs, TEAEs, treatment-related TEAEs, TEAEs by severity, SAEs, deaths, and AEs leading to discontinuation, will be presented.

All information pertaining to AEs noted during the study will be listed by subject and will include a verbatim description of the event as reported by the investigator, as well as the preferred term, system organ class, start date, end date (if ended), seriousness, severity, action taken regarding the study drug, outcome, and relationship to the study drug. In addition, a listing of subjects who prematurely discontinue from the study due to AEs will be provided.

SAEs will be listed and summarized in a similar manner to AEs.

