#### 2. INTRODUCTION

The MTI-107 study described herein is an open-label study to assess the long-term safety of serlopitant in adults with pruritus associated with prurigo nodularis (PN), atopic dermatitis (AD), or psoriasis.

Subjects enrolled in MTI-107 may have or may not have participated in previous Menlo Therapeutics Inc. studies. Previous study participation includes studies in PN (MTI-105, MTI-106, TCP-102), in AD (MTI-103) and in psoriasis (MTI-109).

The MTI-107 study has been terminated early by Sponsor. The Statistical Analysis Plan has been updated to facilitate an abbreviated clinical study report.

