### 6.1.5 Handling of Dropouts or Missing Data

Summary statistics will generally be reported based upon observed data. Should a determination of treatment period (on treatment, pre-treatment, post-treatment) be required for AEs or concomitant medication but the corresponding date is missing, or is a partial date, the event/medication will be considered on treatment unless the portions of the date that are available indicate this is not possible.

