Table 14.1.1.1: Summary of Subject Demographics (Safety Population)
(Page 1 of 2)

	Serlopitant 5 mg
	(N=xxx)
Age (years)	
n	XXX
Mean	XX.X
SD	XX.XX
Median	XX.X
Min. to Max.	xx to xx
Sex	
n	XXX
Male	xx ( xx.x%)
Female	xx ( xx.x%)
Ethnicity	
n	XXX
Hispanic or Latino	xx ( xx.x%)
Not Hispanic or Latino	xx ( xx.x%)
Race	
n	XXX
American Indian or Alaska Native	xx ( xx.x%)
Asian	$\mathbf{x}\mathbf{x}  (\mathbf{x}\mathbf{x}.\mathbf{x}\%)$
Black or African American	XX (XX.X%)
Native Hawaiian or Other Pacific Islander	XX (XX.X%)
White	XX (XX,X'')
Multiple/Other	$\mathbf{x}\mathbf{x}  (\mathbf{x}\mathbf{x}.\mathbf{x}\%)$
Transpio Onio	AA ( AA.A./0)

Table 14.1.1.1: Summary of Subject Demographics (Safety Population)
(Page 2 of 2)

	Serlopitant 5 mg (N=xxx)
Height (cm)	(IV AAA)
N	XXX
Mean	XX.X
SD	XX.XX
Median	XX.X
Min. to Max.	xx to xx
Weight (kg)	
n	XXX
Mean	XX.X
SD	XX.XX
Median	XX.X
Min. to Max.	xx to xx

Table 14.3.0.1: Summary of Extent of Exposure (Safety Population)

	Serlopitant 5 mg (N=xxx)
otal Number of Tablets Used	XXX
n	XXX
Mean	XX.X
SD	XX.XX
Median	XX.X
Min. to Max.	xx to xx
otal Number of Days of Exposure	XXX
n	XXX
Mean	XX.X
SD	XX.XX
Median	XX.X
Min. to Max.	xx to xx
Subjects with 6-Month Exposure a	xx ( xx.x%)
Subjects with 1-Year Exposure a	xx ( xx.x%)

<sup>a Subjects considered having 6-Month exposure if date of first dose – date of last dose + 1 is greater than or equal to 182 days.

Subjects considered having 1-Year exposure if date of first dose – date of last dose + 1 is greater than or equal to 358 days, considering the allowable -7 day window for the Week 52 visit.

Table 14.3.1.1.1: Overall Summary of Treatment-Emergent Adverse Events (TEAEs) (Safety Population)

	Serlopitant 5 mg
	(N=xxx)
Subjects with any TEAE	XX ( XX.X%)
Number of TEAEs	XXX
Subjects with any Related TEAE	xx ( xx.x%)
Number of Related TEAEs	XXX
Subjects with any Serious TEAE	xx ( xx.x%)
Number of Serious TEAEs	XXX
Subjects with any Related Serious TEAE	xx ( xx.x%)
Number of Related Serious TEAEs	XXX
Subjects who Died	xx ( xx.x%)
Subjects who Discontinued Study Drug Due to TEAE	xx ( xx.x%)
Maximum Severity by Subject	
Grade 5	$XX \left( XX.X^{0}/_{0} \right)$
Grade 4	xx (xx.x%)
Grade 3	xx ( xx.x%)
Grade 2	xx ( xx.x%)
Grade 1	xx ( xx.x%)
Maximum Relationship by Subject	
Likely Related	xx ( xx.x%)
Likely Unrelated	xx ( xx.x%)

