Table 14.3.1.1.2.1: Summary of Subjects Reporting Treatment-Emergent Adverse Events (TEAEs) by MedDRA System Organ Class and Preferred Term (Safety Population)

(Page 1 of xx)

System Organ Class a Preferred Term	Serlopitant 5 mg (N=xxx)
Total	xx ( xx.x%)
System Organ Class Preferred Term Preferred Term Preferred Term Preferred Term Preferred Term	xx ( xx.x%) xx ( xx.x%) xx ( xx.x%) xx ( xx.x%) xx ( xx.x%)
System Organ Class Preferred Term Preferred Term Preferred Term Preferred Term Preferred Term	xx ( xx.x%) xx ( xx.x%) xx ( xx.x%) xx ( xx.x%) xx ( xx.x%)

<sup>a Counts reflect numbers of subjects reporting one or more TEAEs that map to MedDRA. At each level of summarization (System Organ Class or Preferred Term) subjects are counted once.

MedDRA Version 21.1.

Table 14.3.1.1.3.1: Summary of Treatment-Emergent Adverse Events (TEAEs) Leading to Discontinuation of Study Drug (Safety Population)

(Page 1 of xx)

System Organ Class a Preferred Term	Serlopitant 5 mg (N=xxx)
Total	xx ( xx.x%)
System Organ Class Preferred Term Preferred Term Preferred Term Preferred Term Preferred Term	xx ( xx.x%) xx ( xx.x%) xx ( xx.x%) xx ( xx.x%) xx ( xx.x%)
System Organ Class Preferred Term Preferred Term Preferred Term Preferred Term Preferred Term	xx ( xx.x%) xx ( xx.x%) xx ( xx.x%) xx ( xx.x%) xx ( xx.x%)

<sup>a Counts reflect numbers of subjects reporting one or more TEAEs that map to MedDRA. At each level of summarization (System Organ Class or Preferred Term) subjects are counted once.

MedDRA Version 21.1.

Table 14.3.1.1.4.1: Summary of Subjects Reporting Treatment-Emergent Adverse Events (TEAEs) by Severity (Safety Population)
(Page 1 of xx)

System Organ Class a Preferred Term	Serlopitant 5 mg (N=xxx)
Total	
Grade 5	xx (xx.x%)
Grade 4	xx (xx.x%)
Grade 3	xx (xx.x%)
Grade 2	xx (xx.x%)
Grade 1	xx ( xx.x%)
System Organ Class	
Grade 5	xx (xx.x%)
Grade 4	xx (xx.x%)
Grade 3	xx (xx.x%)
Grade 2	xx (xx.x%)
Grade 1	xx ( xx.x%)
Preferred Term	
Grade 5	xx ( xx.x%)
Grade 4	xx (xx.x%)
Grade 3	xx (xx.x%)
Grade 2	xx ( xx.x%)
Grade 1	xx ( xx.x%)

<sup>a Counts reflect numbers of subjects reporting one or more TEAEs that map to MedDRA. At each level of summarization (System Organ Class or Preferred Term) subjects are counted once under the greatest reported severity.

MedDRA Version 21.1.

Grade 1=Mild; Grade 2=Moderate; Grade 3=Severe; Grade 4=Life Threatening; Grade 5=Death.

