# Table 14.3.1.3.1.1: Summary of Subjects Reporting Serious Treatment-Emergent Adverse Events (TEAEs) by MedDRA System Organ Class and Preferred Term (Safety Population) (Page 1 of xx)

System Organ Class a Preferred Term	Serlopitant 5 mg (N=xxx)
Total	xx ( xx.x%)
System Organ Class Preferred Term Preferred Term Preferred Term Preferred Term Preferred Term	xx ( xx.x%) xx ( xx.x%) xx ( xx.x%) xx ( xx.x%) xx ( xx.x%)
System Organ Class Preferred Term Preferred Term Preferred Term Preferred Term Preferred Term	xx ( xx.x%) xx ( xx.x%) xx ( xx.x%) xx ( xx.x%) xx ( xx.x%)

<sup>a Counts reflect numbers of subjects reporting one or more TEAEs that map to MedDRA. At each level of summarization (System Organ Class or Preferred Term) subjects are counted once.

Note: TEAEs are AEs with an onset date after first dose of study drug.

MedDRA Version 21.1.

Table 14.3.1.3.2.1: Summary of Subjects Reporting Serious Treatment-Emergent Adverse Events (TEAEs) by Severity (Safety Population)

(Page 1 of xx)

System Organ Class a Preferred Term	Serlopitant 5 mg (N=xxx)
Total	
Grade 5	xx ( xx.x%)
Grade 4	xx ( xx.x%)
Grade 3	xx ( xx.x%)
Grade 2	xx ( xx.x%)
Grade 1	xx ( xx.x%)
System Organ Class	
Grade 5	xx ( xx.x%)
Grade 4	xx ( xx.x%)
Grade 3	xx ( xx.x%)
Grade 2	xx ( xx.x%)
Grade 1	xx ( xx.x%)
Preferred Term	
Grade 5	xx ( xx.x%)
Grade 4	xx ( xx.x%)
Grade 3	xx ( xx,x%)
Grade 2	xx ( xx.x%)
Grade 1	xx ( xx.x%)

<sup>a Counts reflect numbers of subjects reporting one or more TEAEs that map to MedDRA. At each level of summarization (System Organ Class or Preferred Term) subjects are counted once under the greatest reported severity.

MedDRA Version 21.1.

Grade 1=Mild; Grade 2=Moderate; Grade 3=Severe; Grade 4=Life Threatening; Grade 5=Death.

Table 14.3.1.3.3.1: Summary of Subjects Reporting Serious Treatment-Emergent Adverse Events (TEAEs) by Relationship to Study Drug (Safety Population)

(Page 1 of xx)

System Organ Class a Preferred Term	Serlopitant 5 mg (N=xxx)
Total Likely Related Likely Unrelated	xx ( xx.x%) xx ( xx.x%)
System Organ Class Likely Related Likely Unrelated	xx ( xx.x%) xx ( xx.x%)
Preferred Term Likely Related Likely Unrelated	xx ( xx.x%) xx ( xx.x%)

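### The SAP pools on-drug and post-drug TEAEs in one crude percentage for a trial stopped early, and drops the protocol's period tables without naming them

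*SAP*

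**What the plan says.** Protocol v3.0, 8.8.1, sets out TEAE incidence in layers: "in addition to the TEAE analysis over the entire 12-month treatment time, results will be presented for the following periods". The periods are 0–4, >4–12, >12–28 and >28–36 weeks, then >36 weeks to end of treatment, and finally "end of treatment to end of the study (including by weekly periods from end of treatment to end of study".

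SAP version 4 (12 May 2020), 6.8.2, has one layer: "TEAEs will be tabulated in a manner which provides information about the incidence of TEAEs for the entire study". The note to Table 14.3.1.3.1.1 defines the events: "TEAEs are AEs with an onset date after first dose of study drug". It sets no upper limit at last dose, and protocol 7.2.1 collects AEs through the 5-week follow-up visit. The footnote to the main TEAE table (14.3.1.1.2.1) confirms that entries are subject counts: "Counts reflect numbers of subjects reporting one or more TEAEs that map to MedDRA".

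The context is in SAP section 2: "The MTI-107 study has been terminated early by Sponsor". SAP section 8 names one dropped output, the laboratory graphs, and otherwise says in general terms that analyses were changed for an abbreviated report. SAP 6.1.5 keeps a dating rule that begins "Should a determination of treatment period (on treatment, pre-treatment, post-treatment) be required for AEs", but no planned TEAE table makes that distinction.

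**The concern.** TEAE and SAE incidence is the first safety endpoint in SAP 5.2 and serves the primary objective of long-term safety. Where subjects have unequal follow-up, one crude percentage is neither a 1-year risk nor a rate, and it says nothing about when events begin. The protocol's stated reason for the period tables was to show how TEAEs evolve over time.

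Pooling also matters for physical dependence. SAP 5.2 keeps its assessment in the 5-week post-drug period as an endpoint, and protocol 6.2.7 relies partly on review of TEAEs in that window. HADS, ESS, vital signs and ECG are now listings only, so no table of any kind summarises the post-drug weeks.

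**Working it through.** **Text check.** SAP section 9 lists 12 tables, 8 of them AE tables: an overall summary, three for TEAEs or serious TEAEs by severity or relationship pairings plus the serious-event counterparts, by system organ class and preferred term, and by discontinuation. All give subject counts with n (%). None is by onset period, none is restricted to the post-drug weeks, and none has a time denominator. Protocol 8.8.1 asks for five on-treatment periods plus a post-drug period broken down by week.

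The plan states no figure to reproduce. What follows is illustration under assumed values, because the documents give no completion rate or exposure distribution.

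**Inputs.** From the documents: 52 weeks on drug, 5 weeks after, up to 700 subjects. Let f = 5/52 = 0.096. Assumed: hazard L = 0.1 per year, share c completing, and non-completers' exposure uniform over 0–52 weeks.

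**1. Can the pooled figure show a post-drug effect?** Let the post-drug hazard be k times the on-drug hazard, with everyone treated for 52 weeks.
- Pooled = 1 − exp(−0.1(1 + kf)): 10.38% at k = 1, 12.09% at k = 3.
- A constant rate of 0.1(1 + 3f)/(1 + f) = 0.118 per year, with no post-drug effect, also gives 12.09%.
- Post-drug risk = 1 − exp(−0.1kf): 0.96% at k = 1 (6.7 of 700), 2.84% at k = 3 (19.9 of 700, if all are followed).
- If everyone stops at 26 weeks, the pooled figure moves from 5.79% to 7.58%.

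**2. How far is the crude figure from a 1-year on-drug risk?** Constant hazard: crude = 1 − [c·exp(−L(1 + f)) + (1 − c)·exp(−Lf)·(1 − exp(−L))/L], against 1 − exp(−0.1) = 9.52%. Late onset (none before Week 26, then 0.1 per year): against 1 − exp(−0.05) = 4.88%.

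| Share completing | 0 | 20% | 40% | 60% | 80% | 100% |
|---|---|---|---|---|---|---|
| Crude, constant hazard | 5.75% | 6.67% | 7.60% | 8.53% | 9.46% | 10.38% |
| Ratio to 9.52% | 0.60 | 0.70 | 0.80 | 0.90 | 0.99 | 1.09 |
| Ratio if non-completers have no post-drug follow-up | 0.51 | 0.62 | 0.74 | 0.86 | 0.97 | 1.09 |
| Crude, late onset | 1.74% | 2.55% | 3.36% | 4.17% | 4.98% | 5.79% |
| Ratio to 4.88% | 0.36 | 0.52 | 0.69 | 0.86 | 1.02 | 1.19 |

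The third row is relevant because protocol 6.4.10 lets the early-discontinuation visit fall anywhere within 35 days of last dose.

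**3. What can a reader recover from the planned tables?** Dividing the crude proportion by mean exposure plus 5 weeks (Table 14.3.0.1 reports "Number of Days of Exposure") gives about 0.995 of the true rate at 0.01 per year and 0.95–0.96 at 0.1. An approximate overall rate is therefore available under a constant hazard. Timing and the on-drug/post-drug split are not.

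**4. Which remedy handles late onset?** One overall on-treatment rate recovers only 0.50/0.67/0.78/0.87/0.94 of the full-follow-up rate at 0/20/40/60/80% completing. Rates within the >28–36 and >36-week periods are 0.1 per year at every completion level. In the last period, n over the number at risk at its start gives 0.50/0.73/0.84/0.92/0.96 of the full-period risk, so subject-time is needed as well. Kaplan-Meier at Week 52, simulated with 2 million subjects, gives 4.86–4.93% at 20–80% completing, against 4.88%.

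**The case against.** Several points on the other side stand:
- Protocol 8.8.1 itself specifies crude subject incidence. It asks for no rates, numbers at risk or Kaplan-Meier estimates, so only the lost periods are a departure from the protocol; the time denominators go further.
- The reduction is disclosed in general terms in SAP section 2, the revision history and section 8. The fault is that the dropped tables are not specified, not that anything was concealed.
- Protocol 6.2.7 describes case-level review, which Listing 16.2.7.1.2 (onset day) together with Listing 16.2.1.1 (last dose) can support.
- The illustration rests on assumed hazards, and the direction of the truncation error depends on completion.
- The 6.1.5 dating rule is conditional and also covers medications, so its survival does not prove that a table was meant.

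Two further arguments concern the split. With a half-life of 45–86 hours, five half-lives are 225–430 hours, or about 9–18 days, and there are long-lived active metabolites, so early post-dose events occur under residual exposure. Rule 6.1.5 also sends ambiguous dates to on-treatment, which lowers the post-drug count. Neither justifies pooling. End of treatment is the protocol's own boundary, weekly post-drug columns would show the washout, and a footnote can give the number of reassigned events. Time denominators are what make period counts readable when follow-up is cut short.

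**Conclusion.** The concern holds. The SAP replaces a period-specific TEAE analysis with one whole-study percentage, and no planned table shows onset period or the post-drug weeks. This should be changed; it is not fatal, because the listings retain the dates and an approximate overall rate can be derived for uncommon terms.

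Under the stated assumptions, a tripled post-drug hazard shifts the pooled figure by only 1.7 percentage points (12.09 − 10.38). The crude figure understates the 1-year on-drug risk when few complete, is close to it at about 80%, and exceeds it when all complete. These are illustrations, not bounds; the actual size depends on exposure data that the documents do not contain.

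**What to change.** Keep n (%). In Tables 14.3.1.1.2.1 (TEAEs) and 14.3.1.3.1.1 (serious TEAEs), restore the protocol 8.8.1 periods, including the post-treatment weeks. For each, give subjects with onset in the period, number at risk at its start, and subject-weeks at risk.

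At minimum, add two columns: on-treatment (first to last dose) and post-last-dose (day after last dose to last visit or contact), each with subject-years at risk and first events per 100 subject-years. For late onset, use the period tables or Kaplan-Meier cumulative incidence at Weeks 26 and 52 where subjects remain at risk; a single on-treatment rate does not address it. Apply 6.1.5 to partial dates and footnote how many AEs it classified. Name any period tables still dropped in SAP section 8.

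A separate correction affects the exposure flags only. SAP 6.8.1 and the Table 14.3.0.1 footnote subtract last dose from first dose. For dosing from Day 1 to Day 364 that gives 1 − 364 + 1 = −362. The result can never exceed 1, so no subject could reach 182 or 358 days. It should be last dose − first dose + 1, here 364.

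The cost is SAP wording, some programming and longer tables in an abbreviated report, with possibly few subjects in late periods. No new data are needed: dose and last-contact dates are in Listing 16.2.1.1, visit dates in 16.2.5.1 and AE start dates in 16.2.7.1.2.

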7.2 Methods and Timing for Recording and Reporting Adverse Events

7.2.1 Adverse Event Reporting Period

Any AE occurrence during the study must be recorded on source documentation and eCRF at the site, in accordance with protocol instructions.

AEs and SAEs will be recorded from the first study drug administration through the followup visit. After the 5-week follow-up visit, only SAEs that are believed to be drug-related should be reported.

After informed consent, but prior to initiation of study drug, only SAEs considered by the investigator to be caused by a protocol-mandated intervention will be collected (e.g. SAEs related to invasive procedures such as blood collection). These procedure-related SAEs should only be reported on the source documents and SAE form, not on the AE eCRF.

Subjects who undergo Baseline visit procedures but are not enrolled into the study will not have SAEs recorded in the clinical database.

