#### 3. STUDY OBJECTIVES

The primary objective of this study is to assess the long-term safety of serlopitant in adults with pruritus associated with PN, AD, or psoriasis.

The secondary objectives of this study are to assess the change in severity of pruritus in subjects with PN, AD, or psoriasis using the worst-itch numeric rating scale (WI-NRS); to assess the change in severity and extent of PN using the Investigator's Global Assessment of PN Stage

Statistical Analysis Plan for Menlo Therapeutics Inc. Protocol Number: MTI-107

(IGA PN-S), for those subjects with PN; and to assess whether serlopitant produces physical dependence.

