# 5.2 Safety Endpoints

Safety endpoints include the following:

- Incidence of treatment-emergent adverse events (TEAEs) and serious adverse events (SAEs)
- Changes from baseline in clinical laboratory parameters
- Changes from baseline in vital sign and electrocardiogram (ECG) parameters
- Change from baseline in the Hospital Anxiety and Depression Scale (HADS)
- Change from baseline in the Epworth Sleepiness Scale (ESS)
- Assessment of physical dependence following chronic study drug exposure, in the monitored 5-week post-drug discontinuation period

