#### 6. STATISTICAL AND ANALYTICAL PLANS

# 6.1 General Methodology

All statistical processing will be performed using SAS® Version 9.3 or later, unless otherwise stated. No interim analyses are planned. Endpoints will be summarized with descriptive statistics by visit. For continuous variables, the following information will be presented: n (number of subjects), mean, standard deviation (SD), median, minimum and maximum. For categorical variables, counts and percentages will be presented.

Reported adverse events (AEs), medical history, and prior and concomitant procedures and therapies will be classified on the basis of Medical Dictionary for Regulatory Activities (MedDRA) terminology. Concomitant medications will be classified on the basis of World Health Organization Drug Dictionary (WHO-DD) terminology.

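### SAP version 4 keeps the physical-dependence objective and its 5-week post-drug endpoint, but no planned table separates post-drug from on-drug adverse events

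*SAP*

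**What the plan says.** SAP section 3 retains the secondary objective "and to assess whether serlopitant produces physical dependence". SAP section 5.2 retains the matching endpoint: "Assessment of physical dependence following chronic study drug exposure, in the monitored 5-week post-drug discontinuation period".

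For adverse events, SAP section 6.8.2 states "TEAEs will be tabulated in a manner which provides information about the incidence of TEAEs for the entire study". Where a subject has several events under one system organ class or preferred term, "the subject will be counted only once for that" class or term. The footnote to Table 14.3.1.3.1.1 gives the definition: "TEAEs are AEs with an onset date after first dose of study drug". Protocol version 3.0, section 7.2.1, sets the collection window: "AEs and SAEs will be recorded from the first study drug administration through the followup visit".

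Protocol section 8.8.1 planned TEAE results for six periods as well as overall. The last of these was "end of treatment to end of the study (including by weekly periods from end of treatment to end of study").

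SAP section 6.1 says "Endpoints will be summarized with descriptive statistics by visit". Sections 6.1.2, 6.7 and 6.8.3 to 6.8.4.6 say instead that no change-from-baseline summaries will be made and that efficacy, laboratory, ECG, vital-sign, HADS and ESS data will be listed. SAP section 8 names one dropped display, the laboratory graphs, and adds a general sentence about the shortened report.

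**The concern.** A dependence question is about what happens after the drug is stopped. A TEAE table that runs from first dose to the follow-up visit cannot show that, because most of the time it covers is on drug. The protocol had a dedicated post-drug period. SAP version 4 removes it while keeping the objective and endpoint it served, and section 8 does not list the removal among the changes. A report that follows the SAP would carry a dependence objective with no tabulated post-drug event rate. A reader of section 6.1 would also expect by-visit summaries that will not exist.

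**Working it through.** The study is single-arm and descriptive, and the documents give no sample-size or power figure to reproduce. The check is a comparison of texts, followed by a labelled illustration.

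**1. Are on-drug and post-drug events pooled?** The TEAE definition starts after first dose and has no upper limit at last dose. Collection runs through the follow-up visit, so post-drug events are in the data. SAP section 9 lists 12 tables, of which eight are TEAE or serious-TEAE tables. Each of the eight has a single whole-study column. Of the six periods in protocol section 8.8.1, none is kept.

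**2. Does the SAP have the means to separate them?** Yes. Section 6.1.5 includes a post-treatment category for adverse events (protocol section 8.1 names only on-treatment and pre-treatment), but no adverse-event table uses it. Section 6.8.1 already uses the last-dose date for exposure.

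**3. What does the count-once rule do?** Within one whole-study window, a post-drug recurrence of a preferred term already reported on drug adds nothing to subject incidence. It adds only to the event-count row of Table 14.3.1.1.1, which is not split by period. A post-drug event with a new preferred term does add to its own row.

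As a bound, assume on-drug incidence of a term is 10% and post-drug incidence lies between 0 and 5%:
- If the two are independent, pooled incidence = 1 − (1 − 0.10)(1 − p), which runs from 10.0% to 1 − 0.90 × 0.95 = 14.5%.
- If every post-drug case already had the term on drug, pooled incidence stays at 10.0% whatever p is.

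**4. Share of observed time.** With T weeks on drug and five weeks after, the post-drug share is 5/(T + 5): 5/57 = 8.8% for T = 52; 5/31 = 16.1% for T = 26; 5/17 = 29.4% for T = 12. Early termination makes T uneven, so the pooled column mixes these shares.

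**5. Illustration (all rates assumed).** Take an event with 10% incidence over 52 weeks at a constant weekly hazard h = −ln(1 − 0.10)/52 = 0.2026%. Let the hazard after stopping be kh, with k = 1 (unchanged) or k = 3 (tripled), and assume every subject is followed for the full five weeks.
- Pooled incidence = 1 − exp(−(T + 5k)h)
- Post-drug incidence = 1 − exp(−5kh)

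| Weeks on drug | Pooled, k = 1 | Pooled, k = 3 | Post-drug, k = 1 | Post-drug, k = 3 |
|---|---|---|---|---|
| 52 | 10.9% | 12.7% | 1.0% | 3.0% |
| 26 | 6.1% | 8.0% | 1.0% | 3.0% |
| 12 | 3.4% | 5.3% | 1.0% | 3.0% |

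The post-drug figures do not depend on T only because full five-week follow-up is assumed. With an assumed two weeks they would be 1 − exp(−2h) = 0.4% and 1 − exp(−6h) = 1.2%.

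**6. How sparse would the column be?** Expected subjects with this event post-drug are n × [1 − exp(−5kh)]. For assumed n of 100, 200 and 700 (700 being the enrolment cap), that is 1.0, 2.0 and 7.1 for k = 1, and 3.0, 6.0 and 21.0 for k = 3. Per single week the figures are 0.2, 0.4 and 1.4 against 0.6, 1.2 and 4.2. One post-drug column is therefore more useful than weekly cells by preferred term.

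**7. SAP section 6.1 against the rest.** Sections 5.1 and 5.2 list 3 + 6 = 9 endpoints. The table index in section 9 covers one of them, TEAE and SAE incidence. The by-visit sentence in section 6.1 conflicts with the specific sections and with the index.

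**The case against.** The other side has a good deal of ground.

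- The shortening was deliberate and disclosed in the revision history, section 2 and section 8, and the individual sections say which data will only be listed. A reader might infer that replacing tables with listings is itself an error, or that the reduction was concealed. The documents do not support either reading.
- A reader might infer that post-drug events can no longer be identified. They can. Listing 16.2.7.1.2 gives each TEAE's start date and study day, and Listings 16.2.1.1 and 16.2.1.2 give the last-dose date. For complete dates, post-drug onset can be worked out by hand.
- A reader might infer that dependence is no longer assessed at all. Protocol section 6.2.7 rests it on HADS, ESS, vital signs, an ECG, laboratory tests and medical review of post-drug TEAEs. The SAP lists the measured data by nominal visit, and nothing withdraws the medical review. TEAE incidence is one strand of several.
- The illustration rests on assumed rates, numbers and follow-up. In a terminated single-arm study the post-drug column may be thin.
- The sentence in section 6.1 is a leftover. The specific sections and the table index make clear which outputs are planned, so the risk of wrong output is small.

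All of this limits the weight of the point. None of it supplies a post-drug incidence with a denominator, and none explains why the objective and endpoint stand unchanged while section 8 is silent on losing the period that served them.

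**Conclusion.** The point holds in a limited form. SAP version 4 retains a dependence objective and a five-week post-drug endpoint, yet every TEAE table pools on-drug and post-drug events, and the removal of the protocol's post-drug period is not named in section 8. The information is recoverable from the listings; what is missing is a summary with a denominator. That conclusion rests on the text alone.

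The size is illustrative. Under the assumptions of step 5, a tripled post-stopping rate raises pooled incidence by about two percentage points, while a separate column would show a threefold difference. Actual numbers treated, time on drug and length of post-drug follow-up are not in the documents.

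The weight is minor to moderate. The split is worth making because it is cheap and restores a protocol-planned summary for a retained endpoint. The changes to sections 6.1 and 8 are editorial.

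**What to change.** 1. In Tables 14.3.1.1.1 and 14.3.1.1.2.1, split TEAEs into on-treatment (onset up to last dose) and post-drug (onset after last dose). Count each subject once per column, and show the number of subjects observed post-drug as the denominator. Add the last-dose date or a post-drug flag to Listing 16.2.7.1.2. Note that section 6.1.5 assigns events with ambiguous dates to treatment, so the post-drug column may be understated.
2. Correct SAP section 6.1 to say that TEAE and SAE incidence is tabulated and the other endpoints are listed only. In SAP section 8, state that the protocol's other TEAE periods and its remaining summaries are dropped, including the compliance calculation in protocol section 8.6.
3. Optional: by-visit HADS and ESS summaries over the post-drug visits.

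If the split is declined, section 8 should at least say that the TEAE periods are dropped and that dependence will not be summarized.

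The cost is one extra descriptive column in two existing tables, one listing field and some wording. No new data are needed. The column will probably be sparse, and early discontinuers may contribute little. The protocol synopsis gives them post-drug visits through five weeks, but section 6.4.10 schedules one visit within 35 days of last dose and section 6.4.11 times the six post-drug visits from Week 52. Those passages need reconciling, and the denominator would show how much follow-up was obtained.
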